3.2 Primary Study Endpoints

Primary Efficacy End Point: The primary end point is a mean reduction in corneal staining score after 8 weeks of treatment, as measured by Fluorescein and Lissamine dye staining.

Primary Tolerability End Point: The change in the test substance tolerance between Day 1 (post-dose) and at weeks 2, 4, 6 and 8.

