Subjects currently treating oGVHD with corticosteroids and/or Restasis will continue these treatments during the whole study. If patients are wearing contact lenses (Soft bandage contact lenses or PROSE lens), they will be asked to discontinue contact lens wear for 1 month prior to being enrolled (Baseline visit) and will be required to not wear contact lenses for the duration of the study (until week 10 visit). The study doctor will provide advice about decreasing oGVHD symptoms with artificial tears, eyelid massage, or warm compresses.

If the subject agrees to enter the study, the first treatment visit will be scheduled. If a washout period is needed, visit 2 will be after 2 weeks (±4 days). If a washout period is not necessary, visit 2 can be scheduled any time in the next 2 weeks after the screening visit.

6.5.2 Visit 2 Day 1 (Randomization and First treatment visit) Prior to first dose (Baseline)

- Vital Signs (blood pressure taken while subject is relaxed in a sitting position for at least 3 minutes, pulse, temperature, and height and weight (at this visit only).
- BSCVA (Snellen's chart)
- OSDI
- Schirmer 1 test and Fluorescein and Lissamine Dye staining
- Keratograph Oculus Redness Score
 - > Non-invasive Keratography Tear Film Break-up Time (NIKBUT)
 - > Tear Meniscus Height (TMH)
- TearLab Osmolarity Test
- InflammaDry Test for MMP-9 Protein
- Baseline Ophthalmic Examination (slit lamp examination, Ocular surface redness score)
- Tear fluid collection for analysis (PicoGreen, Cellometry)
- Physical Inspection of the Nose and Oropharynx
- Conjunctival and eyelid margin cultures
- Record changes in concomitant medication
- Adverse events since screening visit.

Randomization (by pharmacy)

Investigator/designee administers first dose

Post-Dose

RhDNase treatment for ocular GVHD Version: 10.0; 07-26-2018

Page 30 of 47

- Test Substance Tolerance (Visual Analogue Scale; VAS)
- Subjects will be trained on how to self-administer the study eye drops and be given a sufficient supply to last for 2 weeks to take home.
- Subjects will receive a study diary on which to record the day/time of each dose and any adverse effects.
- Post dose evaluation for any adverse effects.

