6.5.6 Visit 6: Week 8 (± 2 days)

Treatment Visit (after any dose for that day)

- Vital Signs
- OSDI
- Fluorescein and Lissamine Dye staining, and Schirmer 1 test
- Keratograph Oculus Redness Score
 - > Non-invasive Keratography Tear Film Break-up Time (NIKBUT)
 - > Tear Meniscus Height (TMH)
- TearLab Osmolarity Test
- InflammaDry Test for MMP-9 Protein
- Clinical Global Impression, Subject Global Assessment
- Test Substance Tolerance (VAS)
- Ophthalmic Examination (slit lamp examination, Ocular surface redness score)
- Tear fluid collection for analysis (PicoGreen, Cellometry)
- Physical Inspection of the Nose and Oropharynx
- Conjunctival and eyelid margin cultures
- Review the subject's diary and record changes in concomitant medication, deviations from drug schedule and adverse events.

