7.1 Sample Size Determination

The sample size is based on the primary efficacy end point (corneal RBS score) using the following assumptions: (i) mean RBS score in ocular GVHD population = 3.1, (ii) sigma (standard deviation) = 2.5, (iii) expected mean based on 60% effect = 1.24. These assumptions are based on our preliminary data in ocular GVHD patients where we found that treatment with DNase I eye drops reduced RBS score by 80% (mean).²⁵ A total of 30 subjects in each group will be required to detect the difference between groups using a 2-sided two-sample t test with an alpha level of 0.05 and 80% power. We elected to enroll 36 subjects per group.

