7.2 Statistical Methods

Biostatisticians from the Design and Analysis Core (DAC) of UIC-CCTS will perform the analysis. We will assess treatment efficacy based on the intent-to-treat principle using each participant's randomized treatment assignment to define treatment groups and outcomes. Safety variables will be analyzed with regard to treatment that participants actually received (the safety population). One eye (target eye) will be selected at screening visit for statistical comparisons as follows: (i) if only 1 eye meets inclusion criteria, this eye is used; (ii) if both eyes meet inclusion criteria, the eye with the higher RBS score is used; (iii) if both eyes have the same RBS score, then the one with the lower Schirmer I score is used; (iv) if both eyes have same scores, the right eye is used. Secondary analyses will be performed for the non-target eye as well. To assess the effect of treatment, we will compare each outcome measure between rhDNase I (study) vs. Vehicle (control) group over time using general linear mixed model, mixed-effects ordinal logistic regression, and mixed-effects multinomial logistic regression for continuous, ordinal and nominal variables respectively. Treatment, time and their interaction will be included in the model. Missing values of less than 25% will be imputed by using multiple imputations; otherwise will not be included in the analysis. Descriptive statistics will be utilized before the modeling to describe the sample. Assumptions behind each statistical method will be examined. Two-sided Pvalue less than 0.05 would be considered as statistical significance. All the analyses will be conducted by using SAS 9.2 (SAS Inst., Cary, NC).

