9.4.1 Responsibilities of the DSMB

- Review and approve the research protocol(s) and plans for data and safety monitoring.
- Review interim analyses of outcome data and cumulative toxicity data for safety and efficacy to determine whether the trial should continue as originally designed, should be changed, or should be terminated.
- Review and approve the primary trial manuscript(s) with regard to determining that the results are fairly presented and the conclusions appropriate.
- Review proposed modifications to the study prior to their implementation
- Following each DSMB meeting, provide the study leadership and the NEI with written recommendations related to continuing, changing, or terminating the trial.
- **9.5 Safety Review Plan:** Study progress and safety will be reviewed semiannually (and more frequently if needed). Progress reports, including patient recruitment, retention/attrition, and AEs will be provided to the Independent Medical Monitor following each of the semiannual reviews. An Annual Report will be compiled and will include a list and summary of AEs. In addition, the Annual Report will address (1) whether AE rates are consistent with pre-study assumptions; (2) reason for dropouts from the study; (3) whether all participants met entry criteria; (4) whether continuation of the study is justified on the basis that additional data are needed to accomplish the stated aims of the study; and (5) conditions whereby the study might be terminated prematurely. The Annual Report will be sent to the Independent Medical Monitor and will be forwarded to the DMSB, IRB, NEI Official, FDA, and industry collaborator. The PI will also send copies of recommendations and comments from the Independent Medical Monitor or Chair of the DSMB to the NEI Program Officer within 2 months of each monitoring review.

10 Confidentiality

Information about study subjects will be kept confidential and managed according to the requirements of the Health Insurance Portability and Accountability Act of 1996 (HIPAA). Those regulations require a signed subject authorization informing the subject of the following:

- What protected health information (PHI) will be collected from subjects in this study
- Who will have access to that information and why
- Who will use or disclose that information
- The rights of a research subject to revoke their authorization for use of their PHI.

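### Section 7.2 does not say which model term tests week-8 corneal staining and does not adjust for the Day-1 score already collected; naming a baseline-adjusted week-8 comparison is a free gain

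*Combined protocol and SAP*

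**What the plan says.** Section 3.2 defines the primary efficacy endpoint as a mean reduction in corneal staining score "after 8 weeks of treatment, as measured by Fluorescein and Lissamine dye staining".

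Section 7.2, repeated in the Statistical Methodology row of the Study Summary, compares each outcome between arms over time. Continuous outcomes get a general linear mixed model, and the terms are stated once for all outcomes: "Treatment, time and their interaction will be included in the model". Neither place says which term or visit contrast is the primary test, lists a baseline covariate, or says whether the pre-dose score enters as a response or as a covariate.

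The pre-dose score is collected. Section 6.5.2, in the Visit 2 block headed "Prior to first dose (Baseline)", lists "Schirmer 1 test and Fluorescein and Lissamine Dye staining". The only later staining visit is week 8 (section 6.5.6): "Fluorescein and Lissamine Dye staining, and Schirmer 1 test". Staining is also done at screening, where it serves eligibility and choice of the target eye.

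Section 7.1 sizes the trial on a mean of 3.1, an SD of 2.5 and an "expected mean based on 60% effect = 1.24", "using a 2-sided two-sample t test with an alpha level of 0.05 and 80% power". It arrives at 30 per group and enrols 36. Section 7.2 does not adopt that t test as the analysis.

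**The concern.** Staining has a single post-dose visit, so a model over time makes sense only if a pre-dose score is one of the responses. With Day 1 and week 8 as the two responses, the listed terms allow two different tests of treatment.

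- **Interaction.** This tests the between-arm difference in change from Day 1. It is valid, but it subtracts the whole Day-1 score instead of weighting it by how well it predicts week 8. Under randomisation, adjusting for Day 1 is asymptotically at least as efficient.
- **Treatment main effect.** This averages week 8 with a visit at which no drug effect is possible, so the expected difference is halved.

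The plan also does not say whether the screening score is a further time level. Until the primary test is named, the deciding p-value can be chosen after the data are seen, among tests with very different power. A covariate that is already collected also goes unused as a covariate.

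**Working it through.** **Inputs.** From section 7.1: difference 3.1 − 1.24 = 1.86; SD 2.5; two-sided alpha 0.05; 30 per group required, 36 enrolled. The 3.1 and 2.5 are given for the RBS score and are assumed to carry over to the current stain. Assumed, because the documents give no value: correlation rho between Day-1 and week-8 scores of 0.3, 0.5 or 0.7, and equal variances at both visits and in both arms. Power is from the noncentral t distribution with noncentrality difference / (SD × √(2/n)).

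**Step 1: the plan's own figure.** Unadjusted t test, n = 30: noncentrality 1.86 / (2.5 × √(2/30)) = 2.88, df 58, power 80.9%. The stated 30 per group reproduces. At n = 36 the same test has 87.6%.

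**Step 2: the candidate tests.**

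- Change score (interaction): difference 1.86, SD = 2.5 × √(2(1 − rho)) = 2.96 / 2.50 / 1.94, df 2n − 2.
- Week 8 adjusted for Day 1: difference 1.86, residual SD = 2.5 × √(1 − rho²) = 2.38 / 2.17 / 1.79, df 2n − 3, variance multiplied by the small-sample factor 1 + 1/(2n − 4).
- Treatment main effect over the two visits: difference 1.86 / 2 = 0.93, SD of the two-visit average = 2.5 × √((1 + rho)/2) = 2.02 / 2.17 / 2.30, df 2n − 2.

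Example at rho = 0.3, n = 36: the change-score noncentrality is 1.86 / (2.96 × √(2/36)) = 2.67, power 74.9%. The adjusted noncentrality is 1.86 / (2.38 × √(2/36 × 69/68)) = 3.28, power 90.0%.

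**Step 3: results.**

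| | rho 0.3 | rho 0.5 | rho 0.7 |
|---|---|---|---|
| Power, 36 per arm: change score | 74.9% | 87.6% | 98.0% |
| Power, 36 per arm: adjusted for Day 1 | 90.0% | 94.6% | 99.1% |
| Power, 36 per arm: main effect | 48.8% | 43.6% | 39.3% |
| Power, 30 per arm: change score | 66.8% | 80.9% | 95.5% |
| Power, 30 per arm: adjusted for Day 1 | 83.7% | 90.0% | 97.6% |
| n per arm for 80%: change score | 41 | 30 | 19 |
| n per arm for 80%: adjusted for Day 1 | 28 | 23 | 17 |
| n per arm for 80%: main effect | 75 | 87 | 98 |

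Adjustment gains about 15, 7 and 1 points over the change score at 36 per arm, and about 17, 9 and 2 at 30 per arm. Simulation with 20,000 trials per rho at 36 per arm agrees: change score 75.0 / 87.6 / 97.9%, adjusted 90.0 / 94.6 / 99.0%, main effect 49.4 / 43.3 / 39.2%. With no treatment effect, all three reject in 4.8 to 5.2% of trials.

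**Step 4: how far this rests on the RBS figures.** The large-sample variance ratio of adjusted to change score is (1 − rho²) / (2(1 − rho)) = (1 + rho)/2 = 0.65 / 0.75 / 0.85. The relative gain therefore needs neither the SD nor the effect size, only rho and equal variances.

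**Step 5: unequal variances.** If the 60% effect is proportional, so that the treated week-8 SD falls to 2.5 × 0.4 = 1.0 (an assumption), simulation at 36 per arm gives 82.6 / 91.3 / 98.0% for the change score and 98.9 / 99.6 / 100% adjusted. The gain is again about 16, 8 and 2 points.

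**The case against.** The strongest reply is that the plan already implies the right test. Section 3.2 speaks of a reduction, section 7.2 of a comparison over time, and staining has one post-dose visit, so among the three listed terms the interaction is the natural one. On that reading the main-effect figures describe a misreading. This largely stands. The main effect is an unlikely choice, and its low power is a reason to name the test, not a forecast of what would be done. It does not close the gap, because the text still designates no term and does not settle whether screening is a time level.

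A second reply is that the gain depends on a correlation nobody has stated, and that the change score already reaches the plan's 80% target at 36 per arm from rho of about 0.4 (81.1%). That is correct, and near rho = 0.7 the gain is about one point. Adjustment risks little, however. Even at rho = 0, power is 87.1% against 87.6% for the unadjusted week-8 test.

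Third, the absolute powers use RBS figures, while corneal staining is now graded with fluorescein in five zones. That also stands, which is why the variance ratio in step 4 is the safer statement. Section 7.2 further sends ordinal outcomes to a different model, so the new wording should say that the score is analysed as continuous.

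**Conclusion.** The point holds. Section 7.2 and the synopsis name three model terms but no primary week-8 contrast and no baseline covariate, although the Day-1 pre-dose score exists for this endpoint. It is an improvement worth making, not an error in the plan: the interaction test is valid and the sample size in section 7.1 reproduces.

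Against the change score, the large-sample variance falls by 35, 25 or 15% at rho 0.3, 0.5 or 0.7, given equal variances. The powers quoted also rest on the RBS mean and SD carrying over. Confidence is high that the contrast is missing and that adjustment is the better analysis. The size of the gain is uncertain because rho is not in the documents. Simple randomisation without stratification (section 5.3) adds a reason to adjust: at 36 per arm the standard error of a chance Day-1 difference is 2.5 × √(2/36) = 0.59, about 32% of the planned effect (0.59 / 1.86).

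**What to change.** State in section 7.2 and the synopsis that:

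- the primary efficacy test is the rhDNase I minus vehicle difference in target-eye corneal staining score at week 8, adjusted for that eye's Day-1 pre-dose score, by ANCOVA or by the mixed model with a common baseline mean, at two-sided 0.05;
- the score is analysed as continuous, and the adjusted difference is reported with its 95% confidence interval;
- the screening score serves eligibility and target-eye selection only.

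Apply the same adjustment to continuous secondary outcomes that have a Day-1 pre-dose value. For those with several post-dose visits, such as OSDI, also name the visit to be tested.

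The cost is wording in two places and the reviews the protocol already requires. Section 9.4.1 lists among the DSMB's duties "Review proposed modifications to the study prior to their implementation", and section 12 sends amendments to the IRB for approval. The change should be made before unblinding. It needs no new data, visits or patients.

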	8.5.		
	8.6	ADVERSE EVENT REPORTING	
	8.6.		
	8.6.		
	8.6.	-	
	0.0.	8.6.3.1 FOLLOW-UP INFORMATION	
	8.7	STUDY CLOSE-OUT	
	8.7		
	0.7	8.7.1.1 7 CALENDER DAY TELEPHONE OR FAX REPORT.	
		8.7.1.2 15 CALENDER DAY WRITTEN REPORT	
	8.8	FAX NUMBER FOR IND SAFETY REPORTS.	
	8.9	IN CASE OF EMERGENCY	
	8.10	DATA SAFETY MANAGEMENT PLAN	
	8.11	STUDY OVERSIGHT	_
	8.12	REPORTING CHANGES IN STUDY STATUS	
9	DAT	A QUALITY AND SAFETY REVIEW PLAN AND MONITORING	39
	9.1	DATA QUALITY AND MANAGEMENT	39
	9.1	-	
	9.1		
	9.2	SUBJECT ACCRUAL AND COMPLIANCE	
	9.2		

	9.2	2.2 MEASUREMENT AND REPORTING OF PARTICIPANT ADHERENCE TO TREATMENT PROTOCOL	40
g	9.3	STOPPING RULE	40
	9.4	DATA AND SAFETY MONITORING BOARD (DSMB)	40
	9.4		
9	. 5	SAFETY REVIEW PLAN	41
10	CON	NFIDENTIALITY	41
11	sou	JRCE DOCUMENTS	42
1	1.1	RECORDS RETENTION	42
12	ETH	ICAL CONSIDERATIONS	42
13	STU	DY FINANCES	
1	3.1	FUNDING SOURCE CONFLICT OF INTEREST	43
1	3.2	CONFLICT OF INTEREST.	43
1	3.3	SUBJECT STIPENDS OR PAYMENTS	43
14	REF	ERENCES	44
15	APP	ENDIX I	47

SCHEDULE OF VISITS AND PROCEDURES

	gı	(e)	(es)					
	Screening	Day 1 (Pre-Dose)	Day 1 (Post-Dose)	Week 2	Week 4	Week 6	Week 8	Week 10
Informed consent	Х							
Demographic information	Χ							
Medical history/ Con Meds/ Transplant history	Х							
Ophthalmic/ oGVHD history	Χ							
Vital signs		Х		Χ	Χ	X	Χ	Х
Best Spectacle Corrected Visual Acuity		Х						Х
Ocular Surface Disease Index (OSDI)	X	Х		Χ	Χ	X	Χ	Х
Clinical Global Impression (CGI)				Χ	Χ	Х	Χ	Х
Subject Global Assessment (SGA)				Χ	Χ	Χ	Χ	Х
Visual Analogue Scale (VAS)			Х	Х	Х	Х	Х	
Ophthalmic examination (Slit lamp)	Χ	Х		Χ	Χ	Х	Χ	Х
Schirmer 1 test and Fluorescein and Lissamine Dye staining	Х	Х					Х	
Ocular surface Redness (OR) score		Х		Χ	Χ	Χ	Χ	Х
Tear fluid analysis (PicoGreen, Cellometry)		Х					Χ	
Keratograph Oculus Redness Score		Χ			Χ		Χ	
Non-invasive Keratography Tear Film Break-up Time (NIKBUT)		Х			Χ		Χ	
Tear Meniscus Height (TMH)		Χ			Χ		Χ	
TearLab Osmolarity Test		Х			Χ		Χ	
InflammaDry for MMP-9 Protein		Х			Х		Х	
Pregnancy test (urine)*	Х							
Randomization visit		Х						
First study medication		Х						
Drug dispensation visits			Х	Х	Х	Х		
Instruction on study medication self- administration			Х	Х	Х	Х		

Version: 10.0; 07-26-2018

Physical inspection of nose & oropharynx	Х		Х	Х	Х	Х	Х
Adverse Events/ Concomitant Medications	Х	X++	Х	Х	Х	Х	Х
Conjunctival culture**	Х					Х	

^{*}If applicable ++ AEs only

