3.1 General Design

This will be a Randomized controlled trial, in which a total of 72 subjects will be enrolled at 1 clinical site. Subjects will be randomly assigned to one of two groups (#1, #2), with 36 subjects per group. One group will be given placebo (Vehicle eye drops) and the other group will be given eye drops containing the study drug (rhDNase I 0.1%).

Patients with established oGVHD will be approached by a member of the research staff to determine if he/ she might be interested in participating in a research study. If the subject is interested, the research staff member will describe the study. If the subject is willing to enter the study, the study will be discussed and the subject will be asked to sign the informed consent form. Consent will be obtained prior to screening to determine eligibility. Screening procedures include documentation of definite oGVHD. Eligible subjects will be enrolled in the study.

All enrolled subjects will receive their first dose of test medication (placebo/ study drug) on study Day 1 in the doctor's office, and after completion of the study assessments, will have the topical eye drops dispensed for self-administration. See Section 5.4 *Preparation and Administration of Study Drug* for details.

Subjects will be provided with diaries to record the time of each dose and will also be asked to record any adverse symptoms. In addition, they will be asked to make a note of any missed doses together with the reason for the omission. Subjects will return two weeks later on Day 14 for further study assessments, thereafter at 4 weeks, 6 weeks and 8 weeks (the last day of treatment), and again at 10 weeks after two weeks of no treatment with study drug for the final study assessments.

Because NETs have an important role in the innate defense against microbes,³⁵ treatment with DNase I to clear NETs may increase susceptibility to ocular surface infections. Symptom relief is an important goal in patients having dry eyes, with the proviso that treatment does not interfere with pathogen defense. Therefore, we will determine whether DNase I treatment affects the ocular surface microbiome.

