4.4.2 Data Collection and Follow-up for Withdrawn Subjects

If a subject withdraws from the study prior to 8 weeks, the subject will be asked to complete the procedures outlined in the 10 week visit as well as the Test Substance Tolerance scale from 8 weeks, as soon as possible. Subjects who voluntarily withdraw from the study between 8 weeks and 10 weeks will be asked to complete procedures outlined in the 10 weeks visit as soon as possible. Subjects who

are withdrawn due to adverse events will be followed at least until resolution or stabilization of the adverse event.

If the subject remains in the study for safety evaluation, follow-up visits will be scheduled according to the schedule of visits and procedures found in the synopsis.

5 Study Drug

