5.7 Rescue Plan

The research staff, including the PI, will be masked to randomization, thus will not be aware if a particular subject receives study drug or placebo. Subjects will be monitored by the Principal Investigator at each study visit. Any worsening of oGVHD or any adverse event (AEs) will be recorded and in the case of AEs followed to resolution. In case of clinical worsening/ adverse event(s), based on the individual subject's clinical condition, one or more of the following therapeutic decisions may be implemented:

- (1) Increasing the frequency of artificial tears use,
- (2) Increasing the use of anti-inflammatory therapy (Restasis/ corticosteroids),
- (3) Discontinue the study drug.

The decision will be made by the Principal Investigator based on his clinical judgment and the individual subject's clinical condition. If contact lens wear is reinstituted and/or the study drug is discontinued, the subject will be withdrawn from the study. If an adverse event is severe enough to discontinue the subject from the study, the PI may decide to break the subject's randomization code if it seems relevant to the treatment of his/her ocular condition at that time. He/ She will receive the treatment required for his/ her eye condition as per established clinical guidelines.

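### The 25% missing-data rule defines neither its unit nor its denominator, and lets a post-randomisation missing count decide whether or how an endpoint, including the primary, is analysed

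*Combined protocol and SAP*

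**What the plan says.** Section 7.2 states that efficacy follows the intent-to-treat principle and that "we will compare each outcome measure between rhDNase I (study) vs. Vehicle (control) group over time using general linear mixed model", with ordinal and multinomial counterparts for other outcome types. The missing-data rule follows: "Missing values of less than 25% will be imputed by using multiple imputations; otherwise will not be included in the analysis". The synopsis repeats it without further definition, and the plan has no other rule for missing data.

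The primary efficacy endpoint in section 3.2 is the mean reduction in corneal staining score "after 8 weeks of treatment, as measured by Fluorescein and Lissamine dye staining". In the schedule of visits, the row "Schirmer 1 test and Fluorescein and Lissamine Dye staining" is marked at screening, Day 1 before dosing and week 8 only. The visit lists in section 6.5 agree, so there is a single post-baseline value.

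Section 4.4.2 says that if a subject withdraws before week 8, "the subject will be asked to complete the procedures outlined in the 10 week visit", together with the week-8 tolerance scale. The week-10 list in section 6.5.7 contains no dye staining. Section 5.7 adds: "If contact lens wear is reinstituted and/or the study drug is discontinued, the subject will be withdrawn from the study".

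Section 7.3 restricts the analysis population to subjects with at least two weeks of treatment who attended the week-2 visit. Section 7.1 derives 30 subjects per group and then says: "We elected to enroll 36 subjects per group".

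**The concern.** The rule makes the analysis depend on a count that is known only after randomisation and that may itself be related to treatment or response. Subjects can be withdrawn after worsening or adverse events, and those who leave entirely before week 8 have no post-baseline staining value, because the withdrawal visit does not collect one. The primary endpoint is therefore as exposed to the cut-off as any other.

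The sentence can be read in three ways, with different results:

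- **Per outcome (or outcome at a visit).** An endpoint with 25% or more missing is not analysed. The trial could end without a primary efficacy result.
- **Per subject.** Subjects with too many missing values are left out. Randomised subjects are then dropped, against the intent-to-treat statement in the same section.
- **Missing values only.** From 25% upwards the gaps are left unimputed and the model uses the observed data. The endpoint survives, but the method still changes at the cut-off.

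A rule open to three readings can be settled after the data are seen. The cut-off also serves no clear purpose: a likelihood-based mixed model uses all observed data under missing-at-random, and multiple imputation does not require a maximum missing fraction.

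**Working it through.** **Inputs.** Section 3.1: "a total of 72 subjects will be enrolled at 1 clinical site", 36 per group. Section 7.1: control mean 3.1, SD 2.5, treated mean 1.24, two-sided alpha 0.05, 80% power, 30 per group required. Section 7.2: cut-off of 25%.

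**1. The plan's own sample size.** Difference = 3.1 − 1.24 = 1.86; standardised difference = 1.86 / 2.5 = 0.744. The normal formula n = 2(1.96 + 0.842)² / 0.744² gives 28.4, so 29 per group. The exact noncentral t calculation gives 29.35, so 30 per group. The stated 30 reproduces.

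**2. The trigger, per outcome, with the 72 week-8 scores as denominator.** 17/72 = 23.6%, below 25%, so imputed. 18/72 = 25.0%, which is not less than 25%, so the second half of the rule applies.

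**3. What would be set aside at the trigger.** 72 − 18 = 54 observed scores. Power of the two-sample t test (exact noncentral t, standardised difference 0.744):

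| Observed per arm | Power |
|---|---|
| 36 and 36 | 87.6% |
| 30 and 30 | 80.9% |
| 27 and 27 | 76.5% |
| 36 and 18 (all loss in one arm) | 71.5% |

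**4. How likely the trigger is.** The protocol states no dropout rate. The step from 30 to 36 per group would correspond to 1 − 30/36 = 16.7%; that is an inference, and the other rates are assumptions. With independent losses, P(X ≥ 18) for X ~ Binomial(72, p):

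| Assumed loss | Chance of 18 or more missing |
|---|---|
| 15% | 1.8% |
| 16.7% | 4.6% |
| 20% | 17.9% |
| 25% | 54.5% |

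**5. How far the trigger moves with the denominator.**

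- Day 1 plus week 8 values pooled: 2 × 72 = 144, trigger 0.25 × 144 = 36. Eighteen missing is then 12.5% and would be imputed.
- One arm only: 36, trigger 9.
- A section 7.3 population of, for illustration, 68 or 66: trigger 17 (17/68 = 25.0%; 17/66 = 25.8%).

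The same data can fall on either side of the rule, depending on a choice the plan does not make.

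**The case against.** The strongest reply is that the plan never says an endpoint is deleted. Grammatically, what is not included is the missing values, so the sentence can mean that they stay unimputed while the mixed model uses the observed data. That is close to what a statistician would recommend. This stands: a reader might infer that 18 missing scores would delete the primary endpoint as a stated rule, but that is one reading of an undefined sentence, and 18 further assumes the 72 week-8 scores as denominator. Section 7.3, and the provision in section 8.1 for replacing subjects who withdraw because of adverse events, make the count less certain still.

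Other inferences also go too far:

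- **By-arm application.** Nine missing in one arm would trip the rule sooner, but no by-arm rule appears in the text.
- **Every early withdrawal loses the primary value.** Withdrawals between weeks 8 and 10 can already have week-8 staining. Section 4.4.2 keeps subjects who stay for safety evaluation on the visit schedule, and the first two rescue options in section 5.7 do not themselves require withdrawal. The statement holds for subjects who leave entirely before week 8.
- **A direct intent-to-treat contradiction.** Section 7.2 conflicts with intent-to-treat only on the per-subject reading. The explicit exclusion of randomised subjects is in section 7.3.
- **The missing sensitivity analysis.** In a single-centre Phase I/II trial of preliminary efficacy, the absence of an analysis departing from missing-at-random is not an error.

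What the reply does not remove is that, even on its own reading, a post-randomisation count selects the method, and nothing in the plan says that this reading is the intended one.

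**Conclusion.** The concern holds as a defect of definition and of principle, and it should be fixed before unblinding. The rule leaves its unit and denominator open, exempts no endpoint, and on every reading lets observed missingness decide whether or how an endpoint is analysed. Its worst plausible consequence is the per-outcome one: no primary efficacy analysis at 18 missing of 72, despite about 76.5% power in the remaining 54.

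That power figure assumes an even split, missingness unrelated to outcome, and the means and SD of section 7.1, which are stated for the RBS score. The probabilities assume independent losses at rates the documents do not give. At the only rate that can be inferred, 16.7%, the chance is 4.6%. The documents therefore do not support saying that the trial will lose, or is likely to lose, its primary endpoint.

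**What to change.** In section 7.2 and the synopsis, delete the 25% cut-off. State that every endpoint, including the primary, is analysed in all randomised subjects whatever the missing fraction, either with the mixed model on observed data or with multiple imputation, one of the two being chosen in advance. Report missingness by arm for each endpoint. Reconcile section 7.3 with this statement, so that one efficacy population is defined.

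A sensitivity analysis of the primary endpoint that departs from missing-at-random, such as delta-adjusted or vehicle-based imputation, is an optional addition.

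The cost is one sentence replaced in two places, a matching edit to section 7.3 and a table of missingness. No visit, procedure or treatment changes.
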